1.2.2 Secondary estimand(s)

Not applicable.

2 Statistical methods

A CSR will be prepared following the completion of the study. Any data analysis carried out independently by the investigator should be submitted to Novartis before publication or presentation.

2.1 Data analysis general information

The final CSR analysis will be performed by Novartis. SAS version 9.4 or later software will be used to perform all data analyses and to generate tables, figures and listings.

General analysis conventions

Unless otherwise specified: categorical data will be presented as frequencies and percentages; continuous data will be presented as n, mean, standard deviation (SD), median, minimum, and maximum.

For PK concentration and PK parameters, coefficient of variation (CV) (%), geometric mean, and geometric CV% will be presented in addition to the previously mentioned summary statistics.

CV% is calculated as follows:

$$100 * (\text{SD} / \text{arithmetic mean}).$$

Geometric CV (%) is calculated as follows:

$$\text{sqrt}(\exp(\text{variance for log transformed data}) - 1) * 100.$$

Unscheduled assessments

The following points summarize the rules for unscheduled assessments:

- Baseline: All unscheduled assessments before the first dose may be included for consideration when calculating the baseline value.
- In summary tables by visit, unscheduled assessments should not be included unless they qualify as baseline.
- In shift tables and table of abnormal values all unscheduled assessments are included.

Unscheduled assessments will be reported with the scheduled assessments in the listings.

2.1.1 General definitions

2.1.1.1 Investigational drug and study treatment

Investigational drug refers to DFV890, MAS825 or placebo.

Study treatment refers to sc single dose of MAS825, oral daily doses of placebo or DFV890 at various dose levels: MAS825, Placebo, DFV890 10 mg, DFV890 25 mg, DFV890 50 mg and DFV890 100 mg. The start and end of each study treatment refers to that of the dosing period.

2.1.1.2 Treatment sequence

In this study, participants are randomized to either of the five treatment sequences, each contains 4 dosing periods. The study treatment planned for each dosing period within each treatment sequence is shown below:

Treatment sequence 1: MAS825 – Placebo – Placebo – Placebo. Note that the effect of MAS825 is expected to persist over the entire 12-week treatment period. Therefore data collected in this sequence, after week 3 will be still assigned to MAS825.

Treatment sequence 2: Placebo – DFV890 10 mg – DFV890 25 mg – DFV890 100 mg

Treatment sequence 3: Placebo – DFV890 25 mg – DFV890 50 mg – DFV890 100 mg

Treatment sequence 4: DFV890 10 mg – DFV890 25 mg – DFV890 50 mg – DFV890 100 mg

Treatment sequence 5: Placebo – Placebo – Placebo – Placebo

2.1.1.3 Dosing period

A dosing period is defined as an approximate 3-week interval between scheduled visits as given in the study design figure ([Figure 1-1](#)). For example, dosing period 1 will begin at Day 1 (randomization) and it is expected to end on the Day 22 visit, at which point the next treatment will be administered according to the specific treatment sequence. All assessments will be done before the dosing of the next dosing period. Specifically:

Dosing period 1: Begins at Day 1 (randomization) and ends on max (Day 22 visit, last dose in dosing period 1) prior to next dosing level.

Dosing period 2: Begins immediately after the end of dosing period 1 and ends on max (Day 43 visit, last dose in dosing period 2) prior to the next dosing level.

Dosing period 3: Begins immediately after the end of dosing period 2 and ends on max (Day 64 visit, last dose in dosing period 3) prior to the next dosing level.

Dosing period 4: Begins immediately after the end of dosing period 3 and ends on max (Day 85 visit, last dosing in period 4).

The Follow-up period begins immediately after the last dosing period.

2.1.1.4 Date of first administration of investigational drug

The date of first administration of investigational drug is defined as the first date when a nonzero dose of investigational drug is administered and recorded on dose administration CRF. The date of first administration of investigational drug will also be referred as start of investigational drug. Date of first administration of investigational drug will also be defined at the dosing session level.

2.1.1.5 Date of last administration of investigational drug

The date of last administration of investigational drug is defined as the last date when a dose of investigational drug is administered and recorded on dose administration CRF. The date of last administration of investigational drug will also be referred as end of investigational drug.

Date of last administration of investigational drug will also be defined at the dosing session level.

2.1.1.6 Date of first administration of study treatment

See [Section 2.1.1.4](#)

2.1.1.7 Date of last administration of study treatment

See [Section 2.1.1.5](#)

2.1.1.8 Study day

Study Day 1 for all assessments is taken to be the date of first administration of study treatment.

The study day for all assessments will be calculated as follows:

1. If date of assessment occurred on or after the start of study treatment, then
Study day = Date of assessment - Start of study treatment + 1.
2. If date of assessment occurred before the start of study treatment, then
Study day = Date of assessment - Start of study treatment.

If an event starts before the reference start date, the study day will be negative

The study day will be displayed in the data listings and used in outputs, often in the form of planned study day, by treatment sequence.

Study day will also be defined at the dosing period level, that is to say, taking into account the date of first dosing within each treatment period. This alternative definition will be used in outputs by treatment.

2.1.1.9 Baseline

If not stated otherwise, the last available assessment prior to dosing on Day 1 is taken as baseline assessment. Each participant has one baseline value for each parameter.

All unscheduled assessments before the first dose should be included for consideration when calculating the baseline value.

In rare cases where multiple measurements meet the baseline definition, with no further flag or label that can identify the chronological order, then the following rule should be applied: If values are from central and local laboratories, the value from central assessment should be considered as baseline. If multiple values are from the same laboratory (local or central) or collected for ECGs or vital signs, then the median should be considered as baseline.

If participants have no value as defined above, the baseline result will be missing.

For hsCRP the baseline value will be derived as the mean of the two planned assessments before dosing, collected at screening visit and at day 1 pre-dose.

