9.3.2 Statistical model, hypothesis, and method of analysis

The primary analysis for DFV890 will assess the effect on the change in IL-6 and IL-18 compared to placebo in a dose-response model, separately for the two biomarkers.

An E_{\max} model will be fit to the post-baseline values for each biomarker, with a random effect (reflecting between-participant variability) on the placebo response E_0 and on ED_{50} (the dose that produces half the maximal effect), a covariate on E_0 for the baseline value of the biomarker, and a covariate on ED_{50} for baseline body weight. All biomarker measurements will be logarithm-transformed prior to the analysis.

An additional random effect reflecting between-participant variability on E_{\max} may be incorporated if the data allows.

Additional details of the model will be specified in the Statistical Analysis Plan (SAP).

From the model, the predicted response at each treatment and associated 80% CI will be extracted, along with the difference to placebo for each DFV890 dose level, the corresponding 2-sided 80% CI. The estimated response and the difference to placebo will be back-transformed and reported on the ratio scale.

In case of convergence issues, a linear mixed effects model will be fit in place of the E_{\max} model (to be referred to as 'traditional model'). The model will include treatment as a fixed effect, a random intercept effect for participant, and the baseline value of the biomarker and baseline body weight as covariates. All biomarker measurements will be logarithm-transformed prior to the analysis.

The least square (LS) mean and associated 80% CI for each treatment, and the estimated mean difference to placebo for each DFV890 dose level and 2-sided 80% CI will be extracted from the model and back-transformed to the ratio scale for reporting.

The primary analysis for MAS825 will assess the effect on the change in IL-6 compared to placebo after 3 weeks of treatment. For this analysis, the Week 3 measurements of IL-6 on MAS825 and all Week 3 (i.e., Dosing Period 1) placebo measurements from the other sequences will be used.

A linear model of IL-6 at Week 3 with treatment as a fixed effect, and the baseline value of the biomarker as a covariate will be used for the analysis. All biomarker measurements will be logarithm-transformed prior to the analysis.

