2.5.1 Primary endpoint(s)

The primary endpoints are the change from baseline in log transformed serum levels of IL-6 and IL-18 at 3 weeks after the start of a dosing period. Screening and follow-up assessments will be listed and summarized, while the statistical analysis, described in the next section, will include only the assessments taken at the end of each dosing period and the baseline as a covariate. Individual plots by treatment and by treatment sequence will also be provided.

Summaries of descriptive statistics by time will be provided by treatment and by treatment sequence. Summary statistics by sequence will also be used to investigate the presence of potential period/carry-over effects.

Descriptive analyses will also be provided by subgroup (see [Section 2.2.1](#)).

The definition of the primary estimand is provided in [Section 1.2.1](#)

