 - IL-6 reduction $\geq 20\%$ + IL-18 reduction $\geq 10\%$, or
 - IL-6 reduction $\geq 15\%$ + IL-18 reduction $\geq 20\%$.
2. For any of the above criteria that are achieved, the one-sided p-value for the comparison of DFV890 vs. placebo for the associated biomarker(s) is less than 0.1.

A plot showing predicted responses at each treatment and associated 80% confidence interval (CI) as well as the observed mean response will be provided for the selected and the traditional model.

The evaluation of the MAS825 effect will be based on the model described as model 5. This will include a comparison of MAS825 effects vs placebo and comparisons of each DFV890 dose vs MAS825 3 week effect.

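### Averaging the screening and Day 1 values for the IL-6 and IL-18 baseline, as the SAP already does for hsCRP, would be a cheap, modest precision gain for MAS825, provided screening samples were assayed

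*SAP*

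**What the plan says.** The general rule in SAP 2.1.1.9 is that "the last available assessment prior to dosing on Day 1 is taken as baseline assessment", with one baseline value per participant and parameter. Protocol 9.2.1 sets the same default. The SAP departs from it once: "For hsCRP the baseline value will be derived as the mean of the two planned assessments before dosing", meaning screening and Day 1 pre-dose. It makes no such exception for IL-6 or IL-18 and gives no reason for the difference.

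SAP 2.5.1, on the primary endpoints, states that "Screening and follow-up assessments will be listed and summarized", but that the statistical analysis "will include only the assessments taken at the end of each dosing period and the baseline as a covariate". SAP 1.2.1 labels the baseline in the estimand as Day 1.

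For MAS825, protocol 9.3.2 specifies "A linear model of IL-6 at Week 3 with treatment as a fixed effect, and the baseline value of the biomarker as a covariate", and for the comparator "all Week 3 (i.e., Dosing Period 1) placebo measurements from the other sequences will be used". The SAP replaces this: "The evaluation of the MAS825 effect will be based on the model described as model 5". Model 5 is a random-intercept model with baseline biomarker and body weight as covariates. Baseline IL-6 is a covariate in both.

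**The concern.** An exploratory marker gets a two-value baseline while the primary markers get one, although SAP 2.5.1 implies that a second pre-dose value is available. A single reading with within-subject SD 0.4 is a noisy measure of a participant's usual level, and that noise weakens the covariate adjustment.

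The MAS825 contrast is where this matters, because participants in sequence 1 supply no placebo data of their own. Most DFV890 participants do supply placebo data, so those contrasts depend little on the baseline. For MAS825 the point concerns IL-6 only, since IL-18 is a primary endpoint for DFV890 alone. What is at stake is some width of the MAS825 interval and of the comparisons of each DFV890 dose with the MAS825 Week 3 effect.

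**Working it through.** **Inputs.** MAS825 n = 8. Dosing Period 1 placebo comes from sequences 2, 3 and 5 (SAP 2.1.1.2): 8 + 8 + 2 = 18. Effect: 45% reduction, |log 0.55| = 0.598. One-sided alpha 10%. Within-subject SD 0.4 and between-subject SD up to 0.5 (SAP section 3). The documents do not say whether 0.5 is the total SD or only the between-participant component, so both readings are used:
- Reading A: total variance 0.25, of which within 0.16 and between 0.09.
- Reading B: between 0.25, within 0.16, total 0.41 (SD 0.640).

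**The plan's own figure.** SE = SD × √(1/8 + 1/18) = SD × 0.425. Power = Φ(0.598/SE − 1.282).
- A: SE 0.212, power 93.7% (noncentral t 93.1%).
- B: SE 0.272, power 82.0% (noncentral t 81.0%).

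Both meet the stated minimum of 80%.

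**One baseline value against two.** With b the between variance, w the within variance and k baseline values averaged, the residual variance of the Week 3 model is (b + w) − b²/(b + w/k).
- A, k = 1: 0.25 − 0.0081/0.25 = 0.2176 (SD 0.467). k = 2: 0.25 − 0.0081/0.17 = 0.2024 (SD 0.450). Variance −7.0%, log-scale interval width −3.6%. Power 95.9% to 96.8%.
- B, k = 1: 0.41 − 0.0625/0.41 = 0.258 (SD 0.508). k = 2: 0.41 − 0.0625/0.33 = 0.221 (SD 0.470). SE 0.216 to 0.200. Variance −14.3%, width −7.5%. Power 93.2% to 95.7% (noncentral t 92.5% to 95.1%).

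In participants: 26 × (1/0.930 − 1) ≈ 2 and 26 × (1/0.857 − 1) ≈ 4.

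**SAP Model 5.** This is generalised least squares over the five sequences with known variance components, no dropout and body weight omitted. The random-intercept variance after adjustment is b − b²/(b + w/k).
- MAS825 Week 3 against placebo: SE 0.194 to 0.187 (−3.8%) under A; 0.212 to 0.196 (−7.7%) under B.
- DFV890 100 mg against placebo: SE −0.8% (A) and −1.2% (B).

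**Serial correlation.** The figures above treat deviations at different visits as independent, as a random-intercept model does. Suppose instead that within-participant correlation decays exponentially with time (an assumption; the documents give no short-interval correlation) and screening falls 7 to 28 days before Day 1. Let r be the correlation over 3 weeks, c that over the screening gap, and rc that from screening to Week 3. Then:
- one value: (b + w) − (b + wr)²/(b + w);
- two values: (b + w) − (b + w(r + rc)/2)²/(b + w(1 + c)/2).

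Example, B with r = 0.2 and a 21-day gap (c = 0.2, rc = 0.04): 0.41 − 0.282²/0.41 = 0.2160, against 0.41 − 0.2692²/0.346 = 0.2005, a fall of 7.2%.

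| 3-week correlation | Variance change, A | Variance change, B |
|---|---|---|
| 0 | −7.0% | −14.3% |
| 0.1 | −2.4 to −5.2% | −5.9 to −11.6% |
| 0.2 | −1.0 to −2.8% | −3.4 to −8.1% |
| 0.3 | +0.2 to +0.3% | −1.4 to −4.2% |
| 0.4 | +1.5 to +3.6% | +0.2 to +0.3% |
| 0.5 | +2.6 to +7.5% | +1.8 to +4.8% |

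The break-even is about 0.4 under B and just under 0.3 under A.

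**The case against.** The last value before dosing is a conventional baseline, it is the protocol's default, and the power claim is met without any change. All of that stands.

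The strongest objection is that the extra precision is not free. Screening can be up to 30 days before Day 1, so it lies further from Week 3 than the Day 1 value does. The within-subject SD of 0.4 came from placebo data over 24 months and may include slow drift. If deviations persist over weeks, the table shows that a plain average can be worse than Day 1 alone. This also stands, and it is why the Day 1-only analysis should be kept.

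Screening and Day 1 may also reflect different states, because CYP-modulator washout is counted back from Day 1 (protocol 5.2). This carries less weight. Colchicine is restricted relative to screening, and protocol 2.3.1.1 counts immune suppressants back from screening, although Table 6-7 counts from Day 1. No eligibility criterion uses IL-6 or IL-18, so selection on the screening value is not a problem.

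Availability rests on SAP 2.5.1 alone, because the biomarker rows of the assessment schedule are not in the text reviewed.

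A reader might infer that MAS825 is underpowered as planned, for example because power at a 35% reduction would be about 0.75 with one baseline and 0.80 with two (Reading B). The documents do not support that inference: the design effect for MAS825 is 45%, where power is above 90% after baseline adjustment.

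**Conclusion.** This is a worthwhile small improvement, not a flaw. The SAP treats hsCRP and the primary markers differently without explanation. Under the plan's own random-intercept structure with within-subject SD 0.4, averaging would cut MAS825 residual variance for IL-6 by about 7% to 14% and interval width by about 4% to 8%. That is worth roughly 2 to 4 of the 26 participants in the comparison. Power at the planned effect rises by about 1 to 2.5 points, and DFV890 changes by about 1%.

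The conclusion rests on screening IL-6 and IL-18 having been assayed and on only weak week-to-week autocorrelation. Above a 3-week correlation of about 0.3 to 0.4, depending on the between-participant SD, the gain is gone. It would be too strong to say that the planned baseline biases the comparison or that the rule is wrong: where the Day 1 value is missing, it already falls back to an earlier pre-dose value.

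**What to change.** First confirm that screening IL-6 and IL-18 were assayed. If so:
- In SAP 2.1.1.9, define the IL-6 and IL-18 baseline, both as covariate and as change-from-baseline reference, as the mean of the log screening and log Day 1 pre-dose values, or the single available value if one is missing.
- Align the Day 1 wording in SAP 1.2.1. In SAP 2.5.6, state how a participant with one quantifiable value and one below the limit is classed for the supplementary analysis that excludes such baselines.
- Record the departure from protocol 9.2.1 in SAP section 4.
- Keep the Day 1-only baseline as a sensitivity analysis.
- Settle the rule before any unblinded look. SAP 2.13 foresees an unblinded interim assessment of IL-6 and IL-18, and protocol 6.3.2 lets the study statistician see the randomization list at any time.

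The cost is a few sentences and one extra model run per marker, with no new samples. If the sponsor prefers Day 1 alone, one sentence on why hsCRP differs would close the point.

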2.1.1.10 On-treatment period (safety analyses)

On-treatment period starts at day 1 and ends after 30 days from the last dosing.

2.1.1.11 Visit windowing and mapping

Analyses will be conducted according to the planned relative time associated to each visit, except for visits performed after a study drug discontinuation. Post discontinuation visits performed one day after the last dose will be mapped to the corresponding dosing period. Furthermore, if the visit is performed outside the limits described in [Table 1-2](#), PD data collected at that visit will be excluded from the PD analysis set remaining eligible just for supplementary analyses

Other post discontinuation visits will be treated as EOS visits. In case of multiple EOS visits carried-out for the same participant, the visit occurred closer to the planned time (7 days from the last dose) will be considered into the analysis, while data collected in the other visit(s) will be just listed. This is also applicable to the case of participants who discontinued the study treatment still attending all the subsequent visits. Also in this case, visits attended after the study drug discontinuation will be mapped to the end of period, if performed within 1 day from the last dose, to EOS, the one closer to the expected threshold (7 days from the last dose) or excluded from the analysis.

The table below presents some examples:

Table 2-1 Post discontinuation visit mapping

Visit performed after a permanent discontinuation of the study drug	Mapping	Effect on PD analysis set
Within 1 day from the last dose, and after at least 17 days of treatment	Visit mapped to the corresponding dosing period	Data included in the PD analysis set
Within 1 day from the last dose and after < 17 days of treatment	Visit mapped to the corresponding dosing period	Data not included in the PD analysis set (eligible for supplementary analyses)
Not performed within 1 day from the last dose.	Visit mapped to EOS (the closer to the planned time), or excluded from summaries (the further away from the planned time)	Data not included in the statistical Emax/traditional model

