The single s.c. dose of MAS825 [CCI] mg is justified by: the dose is predicted to lead to rapid and [CCI] neutralization of all systemic free IL-1 β and IL-18. The exposure after [CCI] mg s.c. will exceed the in-vitro [CCI] for IL-1 β and IL-18 for more than 150 days after a single dose. The dose and the Cmax is lower than the well tolerated MAS825 dose administered to healthy volunteers with no identified safety concerns ([CCI] mg/kg i.v.). [CCI] (anti-IL-18 mAb) has been administered to healthy subjects in doses up to [CCI] mg/kg i.v. and was well tolerated. Phase 2 studies with [CCI] in [CCI] and [CCI] patients with [CCI] mg/kg i.v. monthly are currently ongoing. In the [CCI] study, an arm with a roughly three fold lower dose of [CCI] mg s.c. monthly is included. In addition, [CCI] (anti-IL1 β mAb) is approved in doses up to 300 mg every 4 weeks. In the MAS825 26-week toxicology study, in non-human primates (marmoset), the highest tested dose, [CCI] mg/kg i.v., [CCI], did not result in any MAS825-related effects.

IG in response to MAS825 [CCI] across different cohorts and time points in the FIH study [CCI]. These results suggest that MAS825 can be safely used for further clinical trials for indications.

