1.2.1 Primary estimand(s)

The primary clinical question of interest is: What is the effect of DFV890 and MAS825 in addition to SoC CVD prevention medication in patients with known coronary heart disease and presence of CHIP on the inflammatory markers IL-6 and IL-18 (IL-18 applicable for DFV890 only), assuming patients continue treatment with reasonable adherence and there are no new major cardiovascular events, initiations of prohibited medication, or febrile infections, but without regard to changes in SoC CVD prevention medication.

The justification for the estimand is that it will capture the effect of the investigational treatments versus placebo under research-like conditions, where participants adhere to their assigned treatment regimen and there is no impact of other intercurrent events on the primary endpoints (aside from potential changes in SoC CVD prevention medication).

The estimand is defined by the following attributes:

- Population: participants with known coronary heart disease and *TET2* or *DNMT3A* CHIP (VAF $\geq 2\%$) and potential SoC CVD prevention medication
- Endpoints: Change from baseline (day 1) in log transformed Serum levels of IL-6 and IL-18 at 3 weeks after the start of a dosing period for DFV890 and serum level of IL-6 at Week 3 for MAS825
- Treatment of interest: MAS825 or placebo single dose, DFV890 QD or DFV890 placebo QD

4. Handling of intercurrent events: see [Table 1-2](#)
5. Summary measure: the model-based difference in variable means between treatments.

Table 1-2 Intercurrent events for the primary estimand

Intercurrent event	Details (if necessary)	Handling of event
Permanent discontinuation of study treatment (DFV890 only)	Potential data collected during an EOT visit will be only used if collected within 1 day from the last dose and if the treatment duration is of at least 17 days in the dosing session affected.	Data collected after this intercurrent event will not be used for this estimand and set to missing
Incidence of a new major CVD event (e.g., myocardial infarction, stroke, etc.)	-	Data collected after this intercurrent event will not be used for this estimand and set to missing
Change in SoC CVD prevention medication	-	All data collected after this intercurrent event will be used for this estimand

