Initiation of a prohibited medication for a comorbid condition	Unforeseen use of any medication expected to have a sustained effect on the primary endpoints (i.e., any systemic corticosteroids)	Data collected after this intercurrent event will not be used for this estimand and set to missing
	Unforeseen use of medication expected to have a limited effect on the primary endpoints (i.e., any other prohibited medications)	Only the assessment immediately following the event will be excluded for the purpose of this estimand and set to missing
New-onset febrile infection	Febrile infection around time of assessment classified as protocol deviation OTH02.	Only the assessment immediately following the event will be excluded for the purpose of this estimand and set to missing
Nonadherence to study treatment (DFV890 only)	Greater than 20% of missed daily doses within 3 weeks prior to an assessment or a treatment duration < 17 days	Only the assessment immediately following the event will be excluded for the purpose of this estimand and set to missing
	Any missed dose within the 2 days prior to an assessment	Only the assessment immediately following the event will be excluded for the purpose of this estimand and set to missing

The handling of each intercurrent event specified in [Table 1-2](#), with the exception of changes in SoC CVD prevention medication, reflects what is referred to as the hypothetical strategy, which aims to mimic a scenario in which the intercurrent event did not actually occur and all participants had adhered to the randomized treatment throughout the course of the study. To enable this strategy, data from various assessments taking place after the event will be excluded from the primary analysis, as described in the table. The exception to this is changes to SoC CVD prevention medication, which will be handled by a treatment policy strategy, in which any occurrence of the event is ignored and the subsequent data are included in the analysis.

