5.5 Rule of exclusion criteria of analysis sets

Criteria leading to exclusion are summarized in the table below. Several exclusions are applied at the epoch level (dosing sessions plus follow-up). More details on protocol deviations are available in the Edit check Document.

Table 5-4 Criteria leading to exclusion

Analysis Set	Criteria that cause subjects to be excluded
Enrolled	Not having informed consent (INCL01) or OTH05 (only screening ECG)
Safety	Not receiving any study drug dose or protocol deviation INCL01 or OTH05 (only screening ECG)
PK	Not member of the Safety or without any valid PK concentration measurement or protocol deviations: WITH01, TRT01, TRT03, OTH01, OTH03

Analysis Set	Criteria that cause subjects to be excluded
PD	Not member of the safety or presenting protocol deviations with a relevant impact on PD (protocol deviations: TRT01, TRT02, TRT05, TRT06, TRT07, TRT08, OTH01, OTH02,)

Where:

OTH05= Screening ECG before ICF Signature. The exclusion is restricted to ECG at screening

WITH01 = sample analyzed after withdrawal of consent

TRT01= treatment deviation with impact on PD and PK analysis for the corresponding treatment period

TRT02= treatment deviation with impact on PD analysis for the corresponding treatment period

TRT03= treatment deviation with impact on PK analysis for the corresponding treatment period

TRT05= Treatment compliance ≥ 60 and $< 80\%$ within 3 weeks prior to an assessment

TRT06= Treatment compliance ≥ 40 and $< 60\%$ within 3 weeks prior to an assessment

TRT07= Treatment compliance ≥ 20 and $< 40\%$ within 3 weeks prior to an assessment

TRT08= Treatment compliance ≥ 0 and $< 20\%$ within 3 weeks prior to an assessment

OTH01= Other deviation with impact on PD and PK analysis for the corresponding treatment period

OTH02= Other deviation with impact on PD analysis for the corresponding treatment period

OTH03= Other deviation with impact on PK analysis for the corresponding treatment period

6 Reference

ICH E9(R1) Harmonized Guideline: addendum on estimands and sensitivity analysis in clinical trials to the guideline on statistical principles for clinical trials. Final version on 20 November 2019.

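### SAP Table 2-1 (and, less firmly, TRT05–TRT08) has no DFV890-only limit, so as written it removes valid MAS825 IL-6 values when placebo tablets are stopped

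*SAP*

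**What the plan says.** **Estimand.** SAP Table 1-2 limits two intercurrent events to one drug: "Permanent discontinuation of study treatment (DFV890 only") and "Nonadherence to study treatment (DFV890 only"). Protocol Table 3-2 applies that limit to nonadherence only. SAP section 4 describes the SAP's differences from the protocol as added detail and clarification.

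**Attribution and model.** SAP 2.1.1.2 keeps Sequence 1 data after week 3 assigned to MAS825. SAP 2.5.2 evaluates MAS825 with model 5, the traditional model, which for IL-6 holds MAS825 at weeks 3, 6, 9 and 12 as four treatment groups.

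**Visit mapping.** The first column of SAP Table 2-1 is headed "Visit performed after a permanent discontinuation of the study drug". A visit not within one day of the last dose is relabelled EOS or left out of summaries, with the consequence "Data not included in the statistical Emax/traditional model". The text of 2.1.1.11 above the table gives the same mapping, also without naming an arm.

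**What counts as a dose.** SAP 2.1.1.1: "Investigational drug refers to DFV890, MAS825 or placebo". SAP 2.1.1.5 takes the last recorded dose of investigational drug as the last administration.

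**PD set.** SAP Table 5-4 lists compliance codes among the PD exclusions. The highest band is "TRT05= Treatment compliance" of at least 60% but under 80%; TRT06 to TRT08 cover the lower bands. No sequence is named.

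**Safety window.** SAP 2.1.1.10: "On-treatment period starts at day 1 and ends after 30 days from the last dosing". SAP 2.7.1 only lists adverse events (AEs) with onset outside that window, yet fixes the MAS825 session at Day 1 to the Day 85 visit.

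**The concern.** A Sequence 1 participant has received all of the active treatment on Day 1. Protocol 7.1 says that discontinuing repeat MAS825 dosing does not apply, and Protocol 4.3 expects exposure to exceed an in-vitro threshold (redacted) "for more than 150 days after a single dose". Whether the participant goes on taking placebo tablets has no bearing on MAS825 exposure.

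Because placebo is investigational drug, the last dose of such a participant is a placebo tablet. A programmer following Table 2-1 would therefore delete IL-6 values that Table 1-2 and 2.1.1.2 keep. These values serve a primary objective, in an arm of eight. The same clock sets the end of the AE window.

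**Working it through.** **1. Apply 2.1.1.11 and 2.1.1.10 literally to Sequence 1.** Assume that every visit is attended on its planned day (22, 43, 64, 85, 92). Visits up to one day after the last tablet stay. Of the later visits, the one closest to 7 days after the last tablet becomes EOS and the rest are dropped. EOS values do not enter the model either, since SAP 2.5.1 uses only end-of-period assessments. The on-treatment window ends at last tablet + 30, and the uncovered part of the MAS825 session is max(0, 85 − (last tablet + 30)).

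| Last tablet | Kept in model 5 | Relabelled EOS | Dropped | Window ends | Session days uncovered |
|---|---|---|---|---|---|
| Day 10 | none | 22 | 43, 64, 85, 92 | Day 40 | 45 |
| Day 30 | 22 | 43 | 64, 85, 92 | Day 60 | 25 |
| Day 45 | 22, 43 | 64 | 85, 92 | Day 75 | 10 |
| Day 55 | 22, 43 | 64 | 85, 92 | Day 85 | 0 |
| Day 84 (completer) | 22, 43, 64, 85 | 92 | none | Day 114 | 0 |

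Under Table 1-2, the Day 22, 43, 64 and 85 values would stay in every row. The primary Week 3 value is lost only when tablets stop more than one day before the Day 22 visit. The safety windows disagree only when tablets stop before about Day 55 (85 − 30 = 55).

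**2. Reproduce the stated power.** Inputs from SAP section 3: effect |log 0.55| = 0.598, SD 0.5 (the stated ceiling), one-sided alpha 0.10, 8 MAS825 participants. The comparator is Period 1 placebo from Sequences 2, 3 and 5 (Protocol 9.3.2): 8 + 8 + 2 = 18. With n MAS825 participants:

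- λ = 0.598 / (0.5 × √(1/n + 1/18))
- df = n + 18 − 3 (two groups, one covariate)
- power = probability that a noncentral t with that df and λ exceeds the 0.90 quantile of the central t

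For n = 8, λ = 0.598 / (0.5 × 0.425) = 2.81 and power is 0.931, consistent with the stated figure of at least 80%.

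**3. Remove Week 3 values.** The number of early tablet stops is not in the documents, so n is varied as an assumption.

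| MAS825 n | λ | Power |
|---|---|---|
| 8 | 2.81 | 0.931 |
| 7 | 2.68 | 0.912 |
| 6 | 2.54 | 0.886 |
| 5 | 2.37 | 0.849 |
| 4 | 2.16 | 0.798 |

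This is a Week 3 two-group approximation. Model 5 is a mixed model with up to 24 placebo sessions (SAP 2.4.1), so the table shows the order of the loss, not the power of model 5 itself.

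**The case against.** Several passages suggest that the authors did not intend this.

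- SAP 2.2 has deviations reviewed case by case with Table 1-2 in view, and SAP 5.5 points to an Edit check Document that may set the scope of the codes. This carries weight for TRT05–TRT08, which is why that part of the point is less firm. The review governs analysis-set exclusions for deviations, not the visit mapping.
- SAP 2.1.1.11 cites the Table 1-2 limits and presents Table 2-1 as illustrative. But the citation concerns visits mapped to a dosing period, and the prose states the rule for all other post-discontinuation visits with no arm limit.
- SAP 2.4.1 leaves Sequence 1 out of the compliance summary. That shows intent, but only for that summary; 2.1.1.11 and Table 5-4 have no matching text.
- SAP 2.5.6 adds an analysis of all available data. It is supplementary and removes every intercurrent-event exclusion, so it does not restore the Table 1-2 estimand.
- On discontinuation, Table 2-1 agrees with Protocol Table 3-2, which has no DFV890 limit. This stands: the conflict lies inside the SAP, which added the limit without recording it as a change.

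On safety, the 30-day window matches the protocol's minimum AE monitoring period (Protocol 8.6.1), reaches Day 114 for completers, and leaves later events in the listings.

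A reader might also infer more than the documents support:

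- **That the safety window contradicts Table 1-2.** That table covers the primary estimand only and sets no safety window.
- **That missed tablets trigger Table 2-1.** It requires permanent discontinuation.
- **That power falls below 80% after one or two losses.** This needs a larger SD. With 0.64, which equals √(0.5² + 0.4²), power is 0.81, 0.78 and 0.75 for n = 8, 7 and 6. No such SD is stated for this comparison, and the plan's claim is conditional on an SD of at most 0.5.
- **That the loss is selective.** It could be, but nothing in the documents shows it.

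**Conclusion.** The point holds as an inconsistency inside the SAP with a direct effect on a primary analysis. The mapping rule, read with the definitions of investigational drug and last administration, removes MAS825 IL-6 values that SAP Table 1-2 and 2.1.1.2 retain. TRT05–TRT08 could do the same, subject to the case-by-case review.

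The size depends on how many Sequence 1 participants stop their tablets permanently before the end of treatment, and in particular before the Day 22 visit. At the planned SD, approximate power stays near or above 0.85 until four of the eight Week 3 values are gone, where it is about 0.80. The harm is therefore departure from the SAP's own estimand and avoidable loss of valid data in a small arm; failure of the stated 80% power is not demonstrated.

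The mismatch between SAP 2.1.1.10 and 2.7.1 is separate and smaller. It affects only Sequence 1 participants whose tablets stop before about Day 55, and their later AEs would still be listed.

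**What to change.** 1. State that the 2.1.1.11 / Table 2-1 post-discontinuation mapping and the TRT05–TRT08 PD exclusions apply to Sequences 2–5 only.
2. For Sequence 1, map visits by planned time since the Day 1 injection, whatever the tablet intake.
3. Reconcile SAP 2.1.1.10 with 2.7.1, so that the Sequence 1 on-treatment period for AE summaries covers at least the Day 1–85 MAS825 session.
4. List in SAP section 4 that the DFV890-only limit on permanent discontinuation is an addition to Protocol Table 3-2.

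The cost is SAP wording and the matching programming specifications; no data are lost and no new data are needed. One small downside: participants in Sequence 1 who stop tablets early would have a longer AE counting window than those in Sequences 2–5. A footnote to the AE tables should say so.
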